7.6.2.3 Percentage Endpoints

The percentage of intercourse attempts lasting longer than a predefined threshold during the treatment assessment period will be analyzed by treatment as continuous data.

Analyses will be carried out using a mixed linear model. All analyses should include treatment and baseline IELT as fixed effects and the type of site as a random effect.

7.6.2.4 Missing Data

Sensitivity analyses for the primary endpoint with methods of handling missing data will be specified in the SAP.

7.6.3 Safety Analyses

Safety analyses will be based on all patients included in the safety population.

Changes from baseline will be the absolute changes from baseline:

Change from baseline = raw value – baseline value

Study Drug Administration and Exposure: Study drug administration and exposure will be summarized and listed. Further details on study drug administration and exposure calculation will be given in the SAP.

Medical History: Medical history details recorded at screening will be summarized and listed according to the coded Medical Dictionary for Regulatory Activities (MedDRA) (latest version) by system organ class, preferred term, and treatment group.

Concomitant Medications: Previous and concomitant medications will be summarized according to the WHO Drug Dictionary (WHO-DD). The number and percentage of patients for each treatment group will be presented for previous and concomitant medications.

The patient will record in the LogPad whether he had any alcoholic drinks within 4 hours prior to sexual intercourse.

Adverse Events: Adverse events will be coded according to the coded MedDRA (latest version). Treatment-emergent AEs will be tabulated by system organ class, preferred term, and treatment group. Further details will be given in the SAP on the definition of TEAEs.

The following summary tables will be produced:

- TEAEs
- Serious TEAEs
- TEAEs leading to study drug discontinuation
- Treatment-related TEAEs leading to study drug discontinuation
- Treatment-related TEAEs
- Treatment-related serious TEAEs

All AEs recorded during the study (including non-treatment-emergent AEs) will be listed.

Physical Examination and Vital Signs: Abnormal physical examinations will be listed. Descriptive by-visit summaries of vital signs data will be presented by treatment group (including raw values and change from baseline). Vital signs will include blood pressure, heart rate, and temperature.

Height, Weight, and BMI: Baseline height, weight, and BMI will be summarized and listed. Weight and BMI as well as mean change from baseline will be summarized for Week 8 and end-of-study visits.

ECGs: Descriptive summaries of change in overall assessment of ECG data from baseline to Week 8 and end of study will be presented in a shift table (normal, abnormal [not clinically significant], and abnormal [clinically significant]) by treatment group.

Laboratory Safety Tests: Hematology and clinical chemistry safety tests will be summarized by treatment and visit. Postbaseline visit will include change from baseline. Shift tables displaying baseline versus worst postbaseline results will be provided by treatment group.

PHQ-9: The PHQ-9 is comprised of 9 questions and is used to monitor depression symptoms. All questions elicit responses on an ordered 4-point scale (0-3), which are added together to generate a single summary score. Higher summary scores indicate an increase in depression severity. The questionnaire is administered at baseline, Week 2, Week 4, and Week 8 visits. Total PHQ-9 scores will be summarized by treatment and visit, with the postbaseline visit displaying raw values as well as change from baseline. In addition, responses to the final question “If you checked off any problems, how difficult have these problems made it for you to do your work, take care of things at home, or get along with other people?” will be summarized by visit as frequency data.

Columbia-Suicide Severity Rating Scale (C-SSRS): The C-SSRS is a structured clinical interview used to assess an individual’s behavior to exhibit thoughts or intent to commit suicide. The questionnaire will be completed at baseline and may be administered at other visits thereafter if clinically indicated. Baseline results will be summarized and listed. Postbaseline results will be listed.

International Index of Erectile Function (IIEF): The IIEF is a questionnaire that comprises 15 questions assessing the effect that erection problems have had on the patient’s sex life over the previous 4 weeks. It is administered at baseline, Week 4, and Week 8. Summary statistics will be provided by visit, and questionnaires will be listed in detail.

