1.3.3 Toxicology

Administration of IX-01 to male rats and male dogs were performed per Good Laboratory Practice.

In the toxicology program, IX-01 was orally administered to male rats and dogs for up to 90 days. Adaptive changes related to liver enzyme induction were noted in the liver as well as in the thyroid and pituitary. Deaths observed at doses ≥ 750 mg/kg in the 1-month studies and exploratory rat studies were likely due to hypothermia. In addition to low core body temperature, these deaths were preceded by clinical signs such as decreased blood pressure, decreased respiration rate, and neurological signs in the animals. At 200 mg/kg of IX-01, dogs exhibited potential neurological signs consisting of titubation, prostration, whining, partially closed eyes, tremors, and occasional diarrhea. The no observed adverse effect levels (NOAELs) with repeated administration were 450 mg/kg in rats and 120 mg/kg in dogs. The corresponding C_{max} and AUC values in rats were 10 100 ng/mL (525 ng/mL free) and

140 000 ng × h/mL (7280 ng × h/mL free), respectively, and in dogs were 52 900 ng/mL (5660 ng/mL free) and 778 000 ng × h/mL (83 246 ng × h/mL free), respectively. The NOAEL is based on adverse clinical effects apparently associated with the CNS observed at higher doses.

IX-01 was negative in genetic toxicology testing and presented no phototoxic potential in vitro.

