Patients willing to take part in the study and who are eligible according to the criteria already assessed during the screening visit will be provided with a LogPad and stopwatch. They will complete training on how to use the LogPad during this visit. Once the training is completed, patients will be asked to attempt intercourse with their partners at least 4 times during the 4-week run-in period, to use the stopwatch to time the attempt, and to record the relevant details in the LogPad including whether alcoholic drinks were taken prior to intercourse. At the next study visit (Visit 2), the patient must bring the LogPad to the study site. Further details for LogPad use and instructions are found in the Study Training Manual.

Baseline Visit 2

On Visit 2 (Day 0, Week 0 \pm 7 days from screening), patients will attend the study center, and information and data collected will include the following:

- Assessment of patient eligibility according to the IELT entry criteria. The patient will return the LogPad to the investigator. The LogPad will provide a summary of the IELT data collected during the run-in period and will indicate whether the patient is eligible to continue in the study based on the IELT criteria. (Note: Refer to the Study Training Manual for instructions if a patient does not remember to return the LogPad.)
- The investigator will provide the LogPad back to the patient for completion of the PEP, PGIS, IIEF, and PHQ-9. After completion of these questionnaires, the patient will return

the LogPad to the investigator. The LogPad will provide a further summary that will indicate whether the patient is eligible to continue in the study based on the results of the PEP, IIEF, and PHQ-9. If the patient is not eligible based on these assessments, then he should not be randomized or continued in the study, and the investigator may discuss alternate treatment options.

- Weight.
- Physical examination.
- Recording of vital sign data (heart rate, blood pressure, and oral temperature measurements) and 12-lead ECG.
- Blood sampling for laboratory safety tests (including hematology, clinical chemistry, and coagulation analyses).
- Urinalysis.
- Urine drug screen.
- C-SSRS.
- Adverse events and concomitant medication update.

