- Physical examination. Any changes in physical findings that meet the definition for an AE and that occur after the patient initiates investigational product will be recorded as AEs in the eCRF.
- Blood sampling for laboratory safety tests (including hematology and clinical chemistry analyses).
- Adverse events and concomitant medication update.

Visit 4

- Patients will return to the study center on Day 28 \pm 7 days (Week 4). The patients will be asked for information on any AEs that have occurred or are occurring and concomitant medication usage since Visit 3. The remaining study medication will be collected, and a check of the quantity remaining will be performed. After completion of all assessments, the patient will receive enough medication to take at least another 14 doses of study drug (IX-01 or placebo). Further supplies can be dispensed at this visit based on a discussion between the Investigator and patient but the maximum allowed dose is 1 dose (3 caplets) per day. (Note: Refer to the Study Training Manual for instructions if a patient does not remember to return the LogPad.)
- The patient will return the LogPad.
- The investigator will provide the LogPad back to the patient for completion of the PEP, PGIS, IIEF, and PHQ-9. Once complete, the patient will return the LogPad to the investigator.
- If the results of the PHQ-9 indicate a change in mental condition (or the investigator suspects an adverse change), the investigator should administer the C-SSRS and determine if the patient may remain in the study.
- Physical examination.
- Recording of vital signs data (heart rate and blood pressure measurements).
- Blood sampling for laboratory safety tests (including hematology and clinical chemistry analyses).
- Urinalysis.
- Adverse events and concomitant medication update.

Visit 5 (End of Treatment or Early Termination)

Note that if a patient is discontinued from the study at any time during the treatment period earlier than expected, then he must return to the study site and complete an early termination visit (Visit 5).

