- Patients will return to the study center on Day 56 ± 7 days (Week 8). The patients will be asked for information on any AEs that occurred or are occurring and concomitant medication usage since Visit 4. The patient must return the LogPad. The remaining study medication will be collected. The LogPad will be checked and retained at the study center. (Note: Refer to the Study Training Manual for instructions if a patient does not remember to return the LogPad.)
- The investigator will provide the LogPad back to the patient for completion of the PEP, IIEF, PHQ-9, PGIS and CGIC. After completion, the patient will return the LogPad to the investigator.
- If the results of the PHQ-9 indicate a change in mental condition (or the investigator suspects an adverse change), the investigator should administer the C-SSRS.
- Weight.
- Physical examination.
- Recording of vital sign data (heart rate and blood pressure measurements) and 12-lead ECG.
- Blood sampling for laboratory safety tests (including hematology and clinical chemistry analyses).
- Urinalysis.
- Urine drug screen.
- Adverse events and concomitant medication update.

End of Study Visit 6 (Follow Up)

Patients will return to the study center for a follow-up visit on Day 70 \pm 7 days (Week 10), and the following assessments will be performed approximately 2 weeks after the last visit:

- Weight.
- Physical examination.
- Recording of vital sign data (heart rate and blood pressure measurements) and 12-lead ECG.
- Blood sampling for laboratory safety tests (including hematology and clinical chemistry analyses).
- Urinalysis.
- Adverse events and concomitant medication update.
- C-SSRS, only if clinically indicated per the protocol.

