6.2 Efficacy Assessments

Outcome measures included during treatment include results from the use of the following:

- Stopwatch to measure IELT.
- LogPad (e-diary) to record summary of study drug intake and details of sexual intercourse attempts (including IELT and two PEP questions (control and ejaculation-related personal distress)).
- Responses to the PEP questionnaire.
- Responses to PGIS questionnaire.
- Responses to the CGIC questionnaire.

IELT

The IELT is the time from the start of intercourse (penetration) until ejaculation and is recorded by the patient or partner using the stopwatch provided. At the start of the run-in phase, the patient and partner should decide who will activate the stopwatch and subsequently stop the stopwatch to record the timing of intercourse. The same person should start and stop the stopwatch with every intercourse attempt throughout the study until Visit 5.

LogPad

The LogPad has been specifically designed to enable patients to record details of sexual intercourse attempts and study drug use throughout the study. The key data to be recorded by the patients are date and time of study drug caplets taken, date and time of any intercourse attempt, IELT, level of control of timing of ejaculation; and level of ejaculation-related personal distress. The patient also will use the LogPad at each study visit to complete the PEP, PGIS, IIEF, and PHQ-9 (PEP, PGIS and IIEF are not completed at Visit 3/Week 2). At the final treatment visit (Visit 5 or Early Termination), the CGIC is also collected via the LogPad. For further details of the LogPad design and function, refer to the Study Training Manual.

PEP

The PEP is a widely used self-administered tool that includes measures of perceived control over ejaculation, ejaculation-related personal distress, ejaculation-related interpersonal difficulty, and satisfaction with intercourse. It has been used in many previous studies of PE and is considered validated for this purpose. All of the domains are relevant to a patient with PE, and the instrument has the advantage of being simple and quick to use.¹⁴ In this study an additional exploratory question on bother will be included in the 4-week recall version used at baseline, week 4 and week 8.

PGIS

The Patient Global Impression of Severity is a questionnaire that asks the patient to assess the severity of their condition (categories of response are no PE, mild, moderate, severe).

CGIC

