6.3 Safety Assessments

Adverse Events

The Investigator and study personnel will monitor each patient for AEs occurring throughout the study treatment period. The process of collection and reporting of AEs is described in Section 6.3.1.

Vital Signs

Vital sign measurements will be taken after the patient has been resting in the sitting position for at least 5 minutes and will include diastolic and systolic blood pressure and heart rate. Vital signs may be repeated if clinically significant values are measured. Out-of-range blood pressure or heart rate measurements will be repeated at the Investigator’s discretion especially if the investigator believes that the initial measurements are due to insufficient relaxation or error. Any confirmed, clinically significant vital sign measurements must be recorded as AEs.

Electrocardiogram (ECG)

A single 12-lead ECG will be collected after a 5-minute period of rest and should be completed before any blood collection. If any clinically significant changes in findings are observed versus the predose or baseline visits, they must be documented. If a clinically significant abnormal finding occurs after the patient initiates use of the study drug, then it will be recorded as an AE in the eCRF.

IIEF

The IIEF is a validated 15-item questionnaire that was designed to evaluate sexual function in men with possible erectile dysfunction. The main purpose of including this instrument in this study is to exclude men with coexisting erectile dysfunction at baseline and to check whether erectile dysfunction occurs during the study.¹⁶ As this instrument was designed for use in men with possible erectile dysfunction, the investigator should clarify the meaning of Questions 4, 5, and 15 before the patient completes the questionnaire. The patient should be told that he is being asked to assess whether he can maintain his erection until ejaculation occurs (Questions 4 and 5) and about his confidence to get and keep an erection until ejaculation occurs (Question 15).

Psychological Assessments

The following questionnaire will be self-completed by each patient using the LogPad (e-diary).

- Patient Health Questionnaire (PHQ-9)

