13.1 Appendix 1: Schedule of Events

Table 13-1 Schedule of Events

IX-0105 Study Schedule and Events							
	For Patients on Chronic SSRIs only Prescreening Visit ¹ (Week -8)	Visit 1 ¹ Screening (Week -4)	Visit 2 ² Baseline (Week 0)	Visit 3 ² (Week 2)	Visit 4 ² (Week 4)	Visit 5 or Early Termination ² (Week 8)	Visit 6 Follow Up (Week 10)
Days Post First Dose (Window)	-56	-28 (±3)	0 (±7)	14 (±3)	28 (±7)	56 (±7)	70 (±7)
Informed Consent	X	X ¹					
Medical History and Demography	X	X ¹					
Inclusion/Exclusion Criteria and Eligibility Review	X	X	X ³				
Physical Examination		X	X	X	X	X	X
Height		X					
Weight		X	X			X	X
Blood Pressure and Heart Rate		X	X		X	X	X
Oral Temperature			X				
12-lead ECG (single)		X	X			X	X
Safety Laboratory Tests (Clinical Chemistry, Hematology, and Coagulation ⁴)		X	X	X	X	X	X
Urinalysis		X	X		X	X	X
Serology (HBsAg, HCV Ab, HIV 1, HIV 2)		X					
Urine Drug Screen		X	X			X	
Randomization			X				
e-Diary Supply ⁵		X	X	X	X		
Diary Evaluation ⁵			X	X	X	X	
Study Drug Supply			X	X	X		
Study Drug Compliance				X	X	X	
IIEF ⁶			X		X	X	
PEP ⁶ (with additional question)			X		X	X	

IX-0105 Study Schedule and Events							
	For Patients on Chronic SSRIs only Prescreening Visit ¹ (Week -8)	Visit 1 ¹ Screening (Week -4)	Visit 2 ² Baseline (Week 0)	Visit 3 ² (Week 2)	Visit 4 ² (Week 4)	Visit 5 or Early Termination ² (Week 8)	Visit 6 Follow Up (Week 10)
Days Post First Dose (Window)	-56	-28 (±3)	0 (±7)	14 (±3)	28 (±7)	56 (±7)	70 (±7)
PGIS			X		X	X	
CGIC						X	
PHQ-9			X	X	X	X	
Columbia-Suicide Severity Rating Scale ⁷			X	(X)	(X)	(X)	(X)
Adverse Events			X	X	X	X	X
Concomitant Medications	X	X	X	X	X	X	X

Abbreviations: CGIC, Clinical Global Impression of Change; ECG, electrocardiogram; HBsAg, hepatitis B surface antigen; HCV Ab, hepatitis C virus antibody; HIV, human immunodeficiency virus; IELT, intravaginal ejaculatory latency time; IIEF, International Index of Erectile Function; PEP, Premature Ejaculation Profile; PHQ-9, Patient Health Questionnaire 9; SSRI, selective serotonin reuptake inhibitor.

1. Only patients taking chronic SSRIs will have an additional 4-week washout prior to the 4-week run-in period. They will attend a Prescreening Visit and will return to the site for a complete screening (Visit 1) once their washout period is complete. Informed consent and medical history will be obtained at the Prescreening Visit for patients who are receiving chronic SSRIs.

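### Section 7.6.3 plans a change-from-baseline summary of temperature, but temperature is scheduled only once, before the first dose

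*Combined protocol and SAP*

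**What the plan says.** The analysis text in Section 7.6.3 promises vital sign summaries by visit and treatment group, "including raw values and change from baseline). Vital signs will include blood pressure, heart rate, and temperature". The same section defines change from baseline as the raw value minus the baseline value.

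The data collection text is narrower. In Table 13-1 the row "Oral Temperature" carries a single mark, in the Visit 2 (Week 0) column. Section 6.1 agrees. At Visit 2 it asks for "Recording of vital sign data (heart rate, blood pressure, and oral temperature measurements) and 12-lead ECG". Visit 3 lists no vital signs. Visit 4 asks for "Recording of vital signs data (heart rate and blood pressure measurements", and Visits 5 and 6 each ask for "Recording of vital sign data (heart rate and blood pressure measurements) and 12-lead ECG". Section 6.3 describes vital signs as taken after seated rest of "at least 5 minutes and will include diastolic and systolic blood pressure and heart rate", with no mention of temperature.

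Study drug is first handed out at Visit 2, to be taken later at home, so the one temperature reading precedes any dose. For dose timing, Section 6.2 states: "The key data to be recorded by the patients are date and time of study drug caplets taken".

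**The concern.** A change from baseline needs a later value. None is scheduled for temperature, so a stated safety analysis cannot be carried out for one of its three parameters. The separate SAP, to which the protocol defers many details, cannot repair this, because it cannot analyse readings that were not taken.

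Two things make this more than a stray word. First, the Visit 2 reading has no other stated use: no eligibility criterion in Section 4.1 refers to temperature, and no other analysis draws on it. Second, the development programme has itself followed temperature. Section 1.3.3 reports that rat deaths at 750 mg/kg and above "in the 1-month studies and exploratory rat studies were likely due to hypothermia", and the Phase 1 multiple-dose studies recorded aural temperature at frequent intervals after dosing.

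What is at stake is limited to a descriptive table that contributes to the secondary objective on toleration and safety. Once patients have passed Visits 4 and 5, the missing readings cannot be recovered.

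**Working it through.** The plan gives no figure to reproduce on this point. The check sets the analysis text beside the schedule and counts.

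**Step 1. Scheduled readings (Table 13-1, confirmed against the visit lists in Section 6.1).**

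| Visit | Week | Blood pressure and heart rate | Oral temperature |
|---|---|---|---|
| 1 | -4 | yes | no |
| 2 | 0 (before first dose) | yes | yes |
| 3 | 2 | no | no |
| 4 | 4 | yes | no |
| 5 | 8 | yes | no |
| 6 | 10 | yes | no |

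Post-baseline visits with a reading: temperature 0 of 4; blood pressure and heart rate 3 of 4.

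**Step 2. What Section 7.6.3 can deliver.** For blood pressure and heart rate, raw values and change from baseline are available at Visits 4, 5 and 6. For temperature, only the raw baseline value exists. Change from baseline is undefined at every later visit, for all 220 planned patients.

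**Step 3. Is this a misread table or superseded text?** No. The table, the visit lists and the Section 6.3 description are three separate places, and none schedules a temperature reading after baseline. The revised schedule in Amendment 1.0 keeps the same single mark, and no listed change adds a reading. Section 6.3 allows vital signs to be repeated, but only those it names.

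**Step 4. How informative would added clinic readings be?** Dosing is as needed and is not tied to clinic visits. Inputs: a mean of 14.6 doses over 8 weeks on active drug in the Phase 2a study (Section 1.3.5), and a treatment period of 56 × 24 = 1344 hours. Assumptions: similar use here, visits random relative to dosing, and a window of 6 hours after a dose as a rough marker of "near peak" (Section 1.3.5 puts the peak at about 1 to 2 hours).

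Chance that a reading falls in the window = doses × 6 / 1344.

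- At 14.6 doses: 87.6 / 1344 = 6.5%, or about 66 × 0.065 = 4 of the 66 patients at 1200 mg per visit.
- At 8 doses (one for each of the 8 attempts requested): 48 / 1344 = 3.6%, or about 2 of 66.
- At 56 doses (the permitted maximum of one a day): 336 / 1344 = 25%, or about 16 of 66.

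Across this whole range, most readings would be taken after the window has passed. The documents do not say at what time of day doses or visits occur, so the assumption of random timing cannot be checked.

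**The case against.** The strongest reply is that the data collection text consistently keeps later vital signs to blood pressure and heart rate, and that the odd one out is a single word in a general paragraph of Section 7.6.3. On that view this is an editorial slip, and the proportionate remedy is to delete the word. Much of this stands. The rest of the vital signs table will be populated, no stopping rule or efficacy result depends on temperature, and Step 4 shows that clinic readings would rarely fall near a dose. Physical examination takes place at every post-baseline visit, and symptomatic temperature changes would be recorded as adverse events. What does not stand is the view that nothing needs to change: the protocol collects a baseline value whose only stated use is this summary, and it promises a comparison that its own schedule rules out.

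A reader might infer something stronger, namely that a known hypothermia risk is going unmonitored. The documents do not support that. The single-dose study, with doses up to 2400 mg, reports no effect on core body temperature. The first multiple-dose study, up to 1200 mg daily, reports no treatment-related change in aural temperature, and the sponsor concludes that the rat finding does not carry over to humans. The second multiple-dose study, at 1600 and 2400 mg, recorded aural temperature and reports no clinically significant vital sign changes, though it gives no separate temperature result.

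A reader might also infer that the blood pressure and ECG summaries are defective because they too ignore time since dose. Nothing in this mismatch shows that: those data are collected at the visits where they are to be summarised.

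**Conclusion.** The mismatch is real and follows directly from the text. As written, the temperature change-from-baseline summary in Section 7.6.3 cannot be produced at any of the four post-baseline visits. That conclusion rests on no assumption beyond reading Table 13-1 and Sections 6.1 and 6.3 as they stand.

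Its importance is minor. It affects the temperature part of one descriptive safety summary. Blood pressure and heart rate summaries, efficacy, power and type I error are untouched. The estimate that few added readings would fall near a dose depends on the assumptions in Step 4. It limits how much the added readings could show but has no bearing on the mismatch itself.

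**What to change.** Preferred: add oral temperature to the vital signs already taken at Visits 4 and 5, and at Visit 6 if an off-treatment value is wanted, with matching edits to Section 6.1, Section 6.3 and Table 13-1. Record the clock time of each temperature reading and report beside it the time since last dose, derived from the LogPad dose times. State in Section 7.6.3 that, because dosing is as needed, most readings will fall well after peak exposure and give only limited information on acute temperature effects.

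Alternative: if the sponsor considers the Phase 1 temperature data sufficient, delete temperature from the change-from-baseline summaries in Section 7.6.3 and say why.

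Cost: the first option adds at most 2 × 220 = 440 thermometer readings (3 × 220 = 660 with Visit 6), a clock time for each, and one derived variable. It needs no new visit and no change to dosing, sample size or the primary analysis. The second option costs one edited sentence.
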